3.3 Correlative Studies Background

Correlative studies will be performed on peripheral blood and tumor biopsies, before and after radiation therapy to investigate mechanisms involving potential synergy between RT and CAR T cell therapy. The effectiveness of CAR T cells may depend on the expansion and persistence of CAR T cells in subjects. Therefore, the expansion and persistence will be monitored by flow cytometry and when possible PCR analysis using peripheral blood samples as per standard SOPs. Samples will be collected per the protocol Schedule of Events (see **11.1 Schedule of Events**). Periodic monitoring of anti-inflammatory cytokines secretion will be performed to determine correlation between CAR T cell effectiveness and/or toxicity and CD19 expression on tumor cells

will be evaluated at the eligibility and in subjects failing following RT.

Additional testing may be done depending on the clinical condition; for instance, patients with an atypical skin rash following RT or other findings that may concern the investigators may have more frequent monitoring to enhance the safety of this trial.

If tumor tissues or bone marrow aspirates become available as part of routine clinical care, a sample will be collected for research analysis. Tissue samples will be analyzed for the presence of CAR-T cells by flow cytometry and/or IHC. Additionally, different T cell subsets may have demonstrated different effector function and persistence and, therefore, T cell immunophenotyping will be performed by flow cytometry. Peripheral blood samples may also be analyzed for cytokine/chemokine levels by Luminex technology. Tumor tissue will be analyzed for CD19 expression by immunohistochemistry and/or flow cytometry. Additional clinical samples testing may be performed based on the Exploratory Endpoints as listed in **Section 2.4**.

All research samples will be delivered, processed, and frozen as per SOP to the [name]/Immune monitoring Laboratory at the MGH Cancer Center for storage and bulk analyses, and pathology samples will be delivered to MGH Pathology Department. Documentation of sample receipt, processing, and storage and primary data from the research analyses will be collected and stored in the processing lab personnel. All research analyses will be performed based on assay-specific SOP using qualified assays.

4. PARTICIPANT SELECTION

All subjects must sign and date the IRB/IEC approved consent form before initiating any study specific procedures or activities that are not part of a subject's routine care. Refer to [Section 10](#) for details.

Each subject who enters the screening period will receive a unique subject identification (**ID**) number before any study specific procedures or activities are initiated. This number will be used to identify the subject throughout the study and must be used on all study documentation related to the subject. Furthermore, the subject identification number must remain constant throughout the entire clinical study, it must not be changed after enrollment or if the subject is rescreened or retreated.

4.1 Diagnosis and selection criteria: refractory hematologic malignancy following any CD19-targeted CAR T cell therapy

Inclusion Criteria

1. Biopsy-confirmed refractory disease within 30 to 90 days following any CD19-targeted CAR T cell therapy for a hematologic malignancy (these include relapsed or refractory large B-cell lymphoma after two or more lines of systemic therapy, including diffuse large B-cell lymphoma (DLBCL) not otherwise specified, primary mediastinal large B-cell lymphoma, high grade B-cell lymphoma, DLBCL arising from follicular lymphoma, and mantle cell lymphoma)

2. At least 1 measurable lesion according to the Lugano criteria¹. Lesions that have been previously irradiated will be considered measurable only if progression has been documented following completion of radiation therapy
3. Toxicities due to prior therapy must be stable and recovered to \leq Grade 1 (except for clinically non-significant toxicities such as alopecia) if there is concern for overlap of anticipated radiation-related toxicity and toxicity from prior therapy due to where the radiation therapy field is located.
4. Age 18 or older
5. Eastern Cooperative Oncology Group (ECOG) performance status of less than or equal to 2.
6. Females of childbearing potential must have a negative serum or urine pregnancy test (females who have undergone surgical sterilization or who have been postmenopausal for at least 2 years are not considered to be of childbearing potential)
7. Ability to understand and the willingness to sign a written informed consent document.

Exclusion Criteria

1. Any medical condition likely to interfere with assessment of safety or efficacy of RT
2. Women of child-bearing potential who are pregnant because of the potentially dangerous effects of the preparative chemotherapy on the fetus or infant. Females who have undergone surgical sterilization or who have been postmenopausal for at least 2 years are not considered to be of childbearing potential
3. In the investigators' judgment, the subject is unlikely to complete all protocol-required study visits or procedures, including follow-up visits, or comply with the study requirements for participation

4.2 Inclusion of Women and Minorities

Both men and women of all races and ethnic groups are eligible for this trial.

5. REGISTRATION PROCEDURES

5.1 General Guidelines for DF/HCC Institutions

Institutions will register eligible participants in the Clinical Trials Management System (CTMS) OnCore. Registrations must occur prior to the initiation of any protocol-specific therapy or intervention. Any participant not registered to the protocol before protocol-specific therapy or intervention begins will be considered ineligible and registration will be denied.

An investigator will confirm eligibility criteria and a member of the study team will complete the protocol-specific eligibility checklist.

Following registration, participants may begin protocol-specific therapy and/or intervention. Issues that would cause treatment delays should be discussed with the Overall Principal

Investigator (PI). If the subject does not receive protocol therapy following registration, the subject must be taken off-study in the CTMS (OnCore) with an appropriate date and reason entered.

5.2 Registration Process for DF/HCC Institutions

Applicable DF/HCC policy (REGIST-101) must be followed.

6. TREATMENT PLAN

6.1 Study treatment

No investigational treatment is included in this study. Radiation therapy is only offered as a standard-of-care treatment.

6.2 Rationale for Study Treatment Dosing

The dose/fractionation of radiotherapy is not being experimentally studied – the radiation oncologist will follow best judgement and International Lymphoma Radiation Oncology Group (ILROG) guidelines for refractory DLBCL (if applicable) to decide on an appropriate, standard of care dose for radiation, regardless of whether or not patient decides to be on the pilot study.

The lesion receiving radiation will be a refractory site of disease following CAR T cell therapy that in most cases, has undergone biopsy, unless an exception is met as per inclusion criteria. For patients with more than one refractory lesion, radiation therapy may be provided to one site only or to a limited number of sites (with only one site getting biopsy). While there is no explicit limit on the number of sites to receive radiation therapy due to patient variety, this decision will be guided based on symptoms due to mass effect, spinal canal or brain involvement, and anticipated toxicity of providing radiation therapy to more than one site. In the vast majority of cases, radiation therapy will be limited to one or two sites.

6.3 Excluded Medications

Corticosteroids and other immunosuppressive drugs should also be avoided for 3 months after CAR T cell administration, unless used to manage CAR T cell-related toxicities. Other medications that might interfere with the evaluation of the investigational product, such as non-steroidal anti-inflammatory agents should also be avoided for the same time period unless medically necessary. Physiologic steroids (less than or equal to 5mg/day) will be allowed on study.

Treatment for lymphoma such as chemotherapy, immunotherapy, targeted agents, radiation, and high dose corticosteroid, other than defined/allowed in this protocol, and other investigational agents are prohibited, except as needed for treatment of disease progression after the CAR T cell infusion and radiation therapy. Patients will be allowed to remain on maintenance therapy (ibrutinib, revlimid, etc) if these medications were initiated prior to and continued during CAR-T infusion.

6.4 Subsequent Therapy

Subsequent therapy administered after the CD19-targeted CAR T cell therapy infusion for a subject's disease, such as non-study specified chemotherapy, immunotherapy, targeted agents, as well as stem cell transplant and radiation therapy, will be recorded until the subject completes the long-term follow-up period, is considered lost to follow-up, withdraws consent, or dies.

6.5 Duration of Follow Up

Long-term Follow-up Period

All subjects who complete the study, and those who withdraw from the study after receiving RT for reasons other than death, will be asked to participate in a long-term follow-up study for up to 6 months after their RT, with a focus on long-term efficacy and safety. These patients will also have long-term follow-up as part of CAR T cell therapy registry. After Month 24 patients will be followed via the CIBMTR immune effector cell therapy registry.

6.6 Criteria for Taking a Participant Off Study

6.6.1 Subject Withdrawal

Subjects have the right to withdraw from the study at any time and for any reason without prejudice to their future medical care by the physician or at the institution.

Subjects can decline to continue to receive study required treatment and/or other protocol required procedures at any time during the study but continue to participate in the study. This is referred to as partial withdrawal of consent.

If partial withdrawal of consent occurs, the investigator must discuss with the subject the appropriate process for discontinuation from protocol required therapies and must discuss options for continued participation, completion of procedures and the associated data collection as outlined in the SOA. The level of follow-up and method of communication should also be discussed between the research staff and the subject and documented in the source documents.

Withdrawal of full consent from a study means that the subject does not wish to receive further protocol required therapy or undergo procedures and the subject does not wish to continue further study follow-up. Subject data collected up to withdrawal of consent will be retained and included in the analysis of the study, and where permitted by local regulations, publicly available data (death records) can be included after withdrawal of consent. The investigator is to discuss with the subject appropriate procedures for withdrawal from the study.

As part of the study sites may be asked to conduct searches of public records, such as those establishing survival status, if available, to obtain survival data for any subject for whom the survival status is not known. Sites may be also asked to also retrieve autopsy reports to confirm status of disease at the time of death.

The investigator and/or sponsor can also decide to withdraw a subject from the investigational product and/or other protocol-required therapies, protocol procedures, or the study as a whole or at any time prior to study completion.

6.6.2 Reasons for Removal from Study

Reasons for removal of a subject from the study are as follows:

- Subject withdrawal of consent from further follow-up
- Investigator decision
- Lost to follow-up
- Death

The reason for taking a participant off study, and the date the participant was removed, must be documented in the case report form (CRF). In addition, the study team will ensure Off Treatment/Off Study information is updated in OnCore in accordance with DF/HCC policy REGIST-101.

7. ADVERSE EVENTS: LIST AND REPORTING REQUIREMENTS

7.1 Expected Toxicities

To date, the following important risks have been identified with axicel and tisacel: CRS, neurologic toxicities, infections, and cytopenias. Grading and management of these toxicities will be performed utilizing the recently released ASTCT CRS/ICANS grading system²¹. Please refer to the current product label for axicel, tisacel, lisocabtagene maraleucel, and brexucabtagene autoleucel for discussion of CRS and neurotoxicity (ICANS). Treatment with RT will occur after 30 day post-infusion period during which centers are FDA mandated to observe for peak toxicities. Additional information and management recommendations can also be found in appendix A. The following are important risks identified with radiation therapy but depend upon the target site for radiation therapy: dermatitis, pneumonitis, esophagitis, fatigue.

7.2 Adverse Events

An adverse event is defined as any untoward medical occurrence in a clinical trial subject. The event does not necessarily have a relationship to treatments provided leading to study eligibility. The investigator is responsible for ensuring that any adverse events observed by the investigator or reported by the subject are recorded in the subject's medical record.

The definition of adverse events includes worsening of a pre-existing medical condition. Worsening indicates that the pre-existing medical condition has increased in severity, frequency, and/or duration or has an association with a worse outcome. A pre-existing condition that has not worsened during the study or involves an intervention such as elective cosmetic surgery or a medical procedure while on study, is not considered an adverse event.

Interventions for pretreatment conditions (such as elective cosmetic surgery) or medical procedures that were planned before study participation are not considered adverse events. Hospitalization for study treatment infusions or precautionary measures per institutional policy are not considered adverse events.

The term “disease progression” as assessed by measurement of malignant lesions on radiographs or other methods should not be reported as adverse events. Death due to disease progression in the absence of signs and symptoms should be reported as the primary tumor type (e.g., B-Cell Lymphoma).

For situations when an adverse event or serious adverse event is due to the disease under investigation report the signs and symptoms. Worsening of signs and symptoms of the malignancy under study should also be reported as adverse events in the appropriate section of the CRF.

The investigators clinical judgment is used to determine whether a subject is to be removed from treatment due to an adverse event. In the event a subject request to withdraw from protocol required therapies or the study due to an adverse event, the subject should undergo the procedures outlined in the Month 3 visit of the SOA.

7.2.1 Definition of Serious Adverse Events

A serious adverse event is defined as an adverse event that meets at least 1 of the following serious criteria:

- Fatal
- Life threatening (places the subject at immediate risk of death)
- Requires in patient hospitalization or prolongation of existing hospitalization
- Results in persistent or significant disability/incapacity
- Congenital anomaly/birth defect
- Other medically important serious event

An adverse event would meet the criterion of “requires hospitalization” if the event necessitated an admission to a healthcare facility (eg, overnight stay).

Events that require an escalation of care when the subject is already hospitalized should be recorded as a serious adverse event. Examples of such events include movement from routine care in the hospital to the ICU or if that event resulted in a prolongation of the existing planned hospitalization.

If an investigator considers an event to be clinically important, but it does not meet any of the serious criteria, the event could be classified as a serious adverse event with the criterion of “other medically important serious event.”

7.3 Adverse Event Characteristics

Adverse Event Assessment

For all AEs, the Investigator must determine both the severity of the AE and the relationship of the AE to CAR T cells treatment. Additionally, patients will also self-report adverse event outcomes pertaining to the region of interest as per their RT treatment field.

- **CTCAE term (AE description) and grade:** All non-CRS/ICANS toxicities will be graded

per CTCAE by the Investigator. The descriptions and grading scales found in the revised NCI Common Terminology Criteria for Adverse Events (CTCAE) version 5.0 will be utilized for AE reporting. All appropriate treatment areas should have access to a copy of the CTCAE version 5.0. A copy of the CTCAE version 5.0 can be downloaded from the CTEP web site:

http://ctep.cancer.gov/protocolDevelopment/electronic_applications/ctc.htm

- **PRO-CTCAE** – Patients will also have the opportunity to self-report adverse event outcomes. The descriptions and grading scales found in the NCI Patient Reported Outcomes Common Terminology Criteria for Adverse Events (PRO-CTCAE) version 1.0 will be utilized. A copy of the possible items for PRO-CTCAE will can be downloaded from the NCI website. Patient will be asked to fill out the applicable section of the survey depending on their radiation treatment site, including items for pain and mood for all patients:
<https://healthcaresdelivery.cancer.gov/pro-ctcae/instrument.html>
- **ASTCT CRS/ICANS:** Any delayed CAR-T related CRS and/or neurotoxicity (ICANS) will be graded using the ASTCT 2019 CRS/ICANS grading system (appendix A).
- **For expedited reporting purposes only:**
 - AEs for agents utilized in this study should be reported only if the adverse event varies in nature, intensity or frequency from the expected toxicity information which is provided.
 - Other AEs for the protocol that do not require reporting are outlined in the next section (Expedited Adverse Event Reporting) and under the sub-heading of Protocol-Specific Expedited Adverse Event Exclusions.
- **Attribution** of the AE:
 - Definite – The AE *is clearly related* to the study treatment.
 - Probable – The AE *is likely related* to the study treatment.
 - Possible – The AE *may be related* to the study treatment.
 - Unlikely – The AE *is doubtfully related* to the study treatment.
 - Unrelated – The AE *is clearly NOT related* to the study treatment.

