The post-CAR T day 30 timepoint represents a unique opportunity to stimulate the immune system and to enhance CAR T-dependent cellular toxicity in a setting in which patients have no reliably effective therapeutic options other than local radiotherapy. These patients may have localized masses in a limited number of sites which are symptomatic or may become symptomatic. Importantly, given the sheer bulk of some of these masses, relapse after CAR T cell therapy remains a concern. Based on a recently presented multicenter retrospective study of chemorefractory high grade B cell lymphoma who underwent axicel, patients with tumor diameter < 5 cm tended to have improved outcomes⁵. In bone marrow transplant patients, for example, radiotherapy is administered for localized refractory/relapsed sites, including bulky masses, in the peritransplant setting⁶. No clinical trials on RT and CAR T cell therapy have yet been published, but Memorial Sloan Kettering⁷ and University of Pennsylvania⁸ are currently studying RT in the pre-CAR T cell therapy bridging setting.

In addition to potential local control benefit, even more exciting is that radiotherapy has the potential to improve immunologic response against cancer cells, to act in synergy with CAR T cell therapy, to produce long term cures. Potential mechanistic reasons for failure following CAR T cell therapy include downregulation of the tumor-associated antigen, mutation of tumor cells to a more rapidly dividing phenotype, and inability of CAR T cells to adapt to a changing tumor-associated antigen repertoire^{1,9}. Low dose radiotherapy may enhance immune-directed tumor death by providing an antigen-independent mechanism of tumor cells resistant to CAR T cell due to downregulation of the receptor against which the CAR T cell are targeted to based on a murine model of pancreatic ductal adenocarcinoma⁷. Based on trials of immune checkpoint inhibitor therapy, RT contributes to immunomodulation by upregulating chemokines, which appears to help T cells locate and infiltrate the tumor, resulting in radiosensitization¹⁰. As such, it is conceivable that radiotherapy may help CAR T cells infiltrate into early refractory disease as at a timepoint that the CAR T cells are still very active.

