7.4 Procedures for AE and SAE Collection and Reporting

7.4.1 Reporting of Adverse Events

The investigator is responsible for ensuring that all adverse events observed by the investigator or reported by the subject that occur from enrollment (ie, radiation therapy consultation) through 3 months after RT are monitored and reported. After 3 months, targeted adverse events including (eg, neurological, hematological, infections, autoimmune disorders, and secondary malignancies) will be monitored and reported for 6 months after treatment with axicel or tisacel or until disease progression, whichever occurs first.

The investigator must address the below for adverse events:

- Adverse event diagnosis or syndrome (if not known, signs or symptoms)
- Dates of onset and resolution
- Severity
- Assessment of relatedness to investigational product, lymphodepleting chemotherapy or study procedures
- Action taken

In reviewing adverse events, investigators must assess whether the adverse event is possibly related to 1) CAR T cell therapy product 2) RT, or 3) any protocol-required study procedure. The relationship is indicated by a yes or no response and entered into the CRF. A yes response should indicate that there is evidence to suggest a causal relationship between the study treatment or procedure and the adverse event. Additional relevant data with respect to describing the adverse event will be collected in the CRFs.

The investigator is responsible for reviewing laboratory test results and determining whether an abnormal value in an individual study subject represents a clinically significant change from the subject's baseline values. In general, abnormal laboratory findings without clinical significance (based on the Investigator's judgment) are not to be recorded as adverse events. However, abnormal laboratory findings that result in new or worsening clinical sequelae, require therapy or adjustment in current therapy are considered adverse events. Where applicable, clinical sequelae (not the laboratory abnormality) are to be recorded as the adverse event.

The investigator is expected to follow reported adverse events until stabilization or resolution. If a subject begins a new anticancer therapy, the adverse event reporting period for non-serious adverse events ends at the time the new treatment is started.

7.4.2 Reporting of Serious Adverse Events and Non-serious CRS events Grade ≥ 3

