			Day 0	Weekly through completion (± 7 days)	Week 1 Post-Treatment (± 7 days)	Week 2 Post-Treatment (± 7 days)	Week 3 Post-Treatment (± 7 days)	Week 4 Post-Treatment (± 7 days)
Day	No longer than 14 days from biopsy and within 28 days of enrollment	Within 14 days of Initiation of Radiotherapy	Day 0	Weekly through completion (± 7 days)	Week 1 Post-Treatment (± 7 days)	Week 2 Post-Treatment (± 7 days)	Week 3 Post-Treatment (± 7 days)	Week 4 Post-Treatment (± 7 days)
Informed consent	X							
Medical history	X							
ECOG Performance Status	X		X	X	X			
CRS/ICANS Consensus Grading	X		X	X				
CTCAE/PRO-CTCAE Surveys		X			X			
Tumor Biopsy	X ^{1,2} (w/in 90 days of CAR T infusion)				X ²			
PET-CT/ disease assessment	X ³							
RT Planning		X						
Physical exam	X			X				
Vital signs (BP, HR, O ₂ sat, temp)	X			X				
Weight (plus Height at screening)	X							
Blood draw for Chemistry panel	X		X	X	X	X	X	X
Blood draw for CBC w/differential	X		X	X	X	X	X	X
Blood draw for C-reactive protein (CRP)	X		X	X	X	X	X	X
Blood draw for Lymphocyte subsets ³			X	X	X	X	X	X
Blood draw for Cytokines ^{4,5}			X	X	X	X	X	X
Blood draw for translational lab collection ^{4,6}			X	X	X	X	X	X
Radiotherapy ⁷			X					
Adverse events/ Concomitant medication	X	X	X	X	X	X	X	X

¹ Tumor biopsy: Either FFPE tumor block or up to 20 unstained slides. Fresh tumor biopsies are preferred however archival tissue is acceptable if obtained prior to screening period but following CAR-T infusion without intervening therapy.

² Tumor biopsy may be deferred if not deemed clinically appropriate and safe.

³ PET-CT (Neck-Chest-Abdomen-Pelvis)/disease assessment: If recent PET-CT performed > 45 days from enrollment, baseline scans must be repeated.

⁴ Prior to radiotherapy on Day 0, then weekly through 4 weeks post radiotherapy.

⁵ Cytokines: 5cc red top tubes

⁶ Translational Labs: Two 10cc purple top tubes

⁷ Radiotherapy: Individual patient course may vary depending on optimal treatment strategy.

⁸ Tumor biopsy: Either FFPE tumor block or up to 20 unstained slides. If possible, repeat tumor biopsy to be obtained in the event of disease progression.

Table 3. Schedule of Assessments (Long-term Follow-up Period)

Procedure	Long Term Follow-up Period (Each visit calculated from CAR-T infusion)		
	Month 6	Month 9	Month 12
Physical exam	X	X	X
CTCAE/PRO-CTCAE Surveys	X	X	X
PET-CT/disease assessment ¹	X		X
Survival Status	X	X	X
Blood draw for CBC w/differential ³	X	X	X
Blood draw for Lymphocyte subsets ³	X	X	X

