12.1 Study Endpoints

Primary Endpoint:

- Rate and severity of RT-related toxicity as per CTCAE v5.0 criteria during RT or within the first 30 days of completing RT.

Secondary Endpoints:

- **Duration of response (DOR):** Among subjects who experience an objective response, DOR is defined as the date of their first objective response (which is subsequently confirmed) to disease progression per Lugano criteria¹ or death regardless of cause. Subjects not meeting the criteria for progression or death by the analysis data cutoff date will be censored at their last evaluable disease assessment date and their response will be noted as ongoing.
- **Objective response rate (ORR) per IRRC:** ORR per IRRC is defined as the incidence of either a complete response or a partial response by Lugano criteria¹ as determined by the IRRC. All subjects that do not meet the criteria for an objective response by the analysis data cutoff date will be considered non-responders.
- **Progression-free Survival (PFS):** PFS is defined as the time from RT completion date to the date of disease progression per Lugano criteria¹ or death from any cause. Subjects not meeting the criteria for progression by the analysis data cutoff date will be censored at their last evaluable disease assessment date.

- **Overall survival (OS):** OS is defined as the time from RT completion to the date of death. Subjects who have not died by the analysis data cutoff date will be censored at their last contact date.

Exploratory Endpoints:

- Levels of anti-CD19 CAR T cells in blood
- Levels of cytokines in serum
- Incidence of anti-axicabtagene ciloleucel antibodies
- Investigation of potential biomarker development based on assessment of blood cells, tumor cells and the proposed actions of the investigational product.

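### As written, the primary toxicity endpoint leaves out RT-attributed CRS and ICANS, and no routine CRS/ICANS grading is scheduled in the four weeks after RT

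*Combined protocol and SAP*

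**What the plan says.** The primary endpoint in section 12.1 is: "Rate and severity of RT-related toxicity as per CTCAE v5.0 criteria during RT or within the first 30 days of completing RT". It names one scale, CTCAE v5.0, and one attribution, to RT.

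Section 7.3 splits grading between two scales. For CTCAE it says "All non-CRS/ICANS toxicities will be graded". For the rest it says "Any delayed CAR-T related CRS and/or neurotoxicity (ICANS) will be graded using the ASTCT 2019 CRS/ICANS grading system".

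In Table 2 the row "CRS/ICANS Consensus Grading" is marked at screening, on Day 0 and weekly through the end of RT. It has no mark in post-treatment Weeks 1, 2, 3 or 4. The row "Adverse events/ Concomitant medication" is marked in every column, including those four weeks. Table 3 (Months 6, 9 and 12) has no CRS/ICANS row.

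Section 7.4.1 covers adverse events "that occur from enrollment (ie, radiation therapy consultation) through 3 months after RT are monitored and reported", and says that "investigators must assess whether the adverse event is possibly related to 1) CAR T cell therapy product 2) RT", or to a study procedure, with a yes or no for each. Section 7.4.2 asks for 24-hour submission of serious events and of non-serious CRS of grade 3 or above. Section 12.4 tabulates all, serious, fatal, CTCAE grade 3 or higher, and treatment-related adverse events.

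**The concern.** The background (3.2.1) presents the early post-CAR T period as a chance to use RT to strengthen CAR T-dependent killing, and suggests that "radiotherapy may help CAR T cells infiltrate into early refractory disease". Section 7.1 names CRS and neurologic toxicity among the important CAR T risks. If RT does increase CAR T activity, CRS or ICANS is a plausible form for the resulting toxicity to take. An endpoint tied to CTCAE does not count it.

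Two things are at stake. The headline RT toxicity rate could be lower than the rate of toxicity that investigators attribute to RT. And section 12.2 says the pilot's toxicity findings will be used to size a larger study, so an understated rate would carry forward.

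**Working it through.** **1. The plan's own figure.** The only computed figure is the required sample size of 19 in 12.2 (95% confidence, interval of 10, population 0.3 × 80 = 24). Reading the interval as ±10 points with p = 0.5:

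- n0 = 1.96² × 0.5 × 0.5 / 0.10² = 96.04
- n = 96.04 / (1 + 95.04/24) = 19.36, which rounds to 19

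It reproduces. The present point does not depend on it and uses only the planned enrollment of 20 as denominator.

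**2. Does CRS/ICANS meet the endpoint definition?**

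- *Scale.* 12.1 requires CTCAE v5.0; 7.3 excludes CRS/ICANS from CTCAE grading. As written it fails.
- *Attribution.* 12.1 requires a relation to RT. 7.3 describes these events as CAR-T related, but 7.4.1 asks about CAR T and RT separately, so an event can be marked as related to both. Attribution alone does not exclude it.
- *Re-entry.* The footnote to the CRS table in Appendix A allows, but does not require, CTCAE grading of organ toxicities that accompany CRS. No section adds ASTCT-graded events to the primary endpoint. The severity cut in 12.4 is also a CTCAE grade, and no ASTCT summary is named there.

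**3. What is scheduled after RT?** Of the four post-RT weekly columns in Table 2, CRS/ICANS grading is marked in 0 and general adverse event collection in 4. The four weeks span about 28 of the 30 post-RT days in the endpoint window. ICANS grading relies partly on the ICE score, an administered test worth 4 + 3 + 1 + 1 + 1 = 10 points, where 7 to 9 is grade 1 (Appendix A). A loss of one to three points may go unnoticed if nobody is prompted to give the test.

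**4. Scale of an omission.** Exact (Clopper-Pearson) 95% limits with n = 20; for 0/20 the upper limit is 1 − 0.025^(1/20) = 0.168.

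| Subjects counted | Rate | Exact 95% limits |
|---|---|---|
| 0/20 | 0% | 0 to 16.8% |
| 1/20 | 5% | 0.1 to 24.9% |
| 2/20 | 10% | 1.2 to 31.7% |

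Each omitted subject is 1/20 = 5 percentage points, but only if that subject has no other counted toxicity at the severity being reported.

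**5. How often could this arise?** The documents give no rate of RT-attributed CRS/ICANS. The rates here are assumptions. The chance of at least one case in 20 is 1 − (1 − p)^20:

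- p = 2%: 33%
- p = 5%: 64%
- p = 10%: 88%
- p = 20%: 99%

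**6. Safety rules.** Section 7.4.4 pauses enrollment after a single grade 4 or higher event related to RT. It lists CRS and neurologic toxicity only under CAR-T-related events, where the trigger is grade 4 or higher for more than 7 days in over 33% of subjects (7 of 20, since 0.33 × 20 = 6.6). The stopping rule in 12.3 refers to grade 4 or higher toxicity attributed to RT and names no scale. Neither section says how a grade 4 CRS or ICANS event attributed to RT would be classified.

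**The case against.** The strongest case against is that little would actually be lost. The grading duty in 7.3 is triggered by the event and has no end date, so a blank cell in Table 2 removes a prompt and not the obligation. Adverse events are collected in all four post-RT weeks and through 3 months, each with an attribution to RT. Section 9.7.4 has weekly visits for a month after RT and lists blood pressure, oxygen saturation and temperature, the measures behind a CRS grade. Grade 3 or higher CRS is reported within 24 hours, and 12.4 tabulates all and treatment-related events. All of this stands. A reader might infer that post-RT CRS/ICANS would go ungraded or be missed by the study; the documents do not support that.

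Table 2 is also weak evidence of intent. It leaves physical examination and vital signs unmarked in the same four weeks although 9.7.4 lists both. That is fair, but 9.7.4 does not list CRS/ICANS grading either, so nothing else fills that gap.

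A reader might further infer that the protocol expects RT to re-activate CAR T cells, or that CRS/ICANS is the toxicity the trial most needs to measure. The protocol says neither. It calls better infiltration conceivable while the cells are still active, and 12.2 puts grade 4 or higher toxicity in the RT field first among its concerns.

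Finally, this is a descriptive pilot with no hypothesis test on this endpoint, so no formal decision is distorted. That lowers the severity. It does not answer the point that no safeguard places an RT-attributed CRS/ICANS event in the primary result.

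**Conclusion.** The point holds in a limited form. Read literally, 12.1 and 7.3 together keep CRS and ICANS out of the primary endpoint even when the investigator attributes them to RT, and Table 2 schedules no routine CRS/ICANS grading in post-RT Weeks 1 to 4. Such events would still be captured elsewhere in the study. The exposure is a primary safety result that need not show them, plus possible under-detection of mild events after RT.

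The size of the bias cannot be estimated from the documents. The 5 points per omitted subject is a scale, not a prediction. It rests on 20 treated subjects and on the omitted subject having no other counted toxicity. The schedule finding assumes that the column positions of the Table 2 marks survived text extraction; the fully marked rows beside it support that reading.

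I rate this as a cheap improvement that should be made, not as a defect that invalidates the plan.

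**What to change.** - **12.1.** State that the primary endpoint also includes CRS and ICANS with onset or worsening from RT start to 30 days after RT that the investigator assesses as possibly related to RT under 7.4.1, whether or not also related to CAR T. Grade them by ASTCT and report them in their own rows beside the CTCAE rates. Label any combined grade 3+ or 4+ rate as using both scales. List CRS/ICANS events judged unrelated to RT separately.
- **Table 2 and 9.7.4.** Mark CRS/ICANS grading at post-RT Weeks 1 to 4, at the weekly visits that already take place.
- **7.4.4 and 12.3.** The pause and stopping rules treat RT-related and CAR-T-related events differently and do not say how an RT-attributed CRS/ICANS event is classified. These passages must be reconciled with each other and with the amended endpoint.

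The cost is a few lines of text, brief grading at existing visits, and a reported toxicity rate that may be higher. The sample size does not change.
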